**Figure 2. Case-crossover study design**

### 6.5.2 Outcomes and follow-up

The primary study endpoint is MACE, defined as the composite of:

- Medically attended non-fatal acute myocardial infarction;
- Medically attended non-fatal stroke;
- Cardiovascular-related death.

The secondary endpoints are:

- Individual components of MACE, analyzed separately, as (1) medically attended non-fatal acute myocardial infarction; (2) medically attended non-fatal stroke; and (3) cardiovascular-related death.

In accordance with the CAMELLIA-TIMI 61 trial, the comparability study will examine safety endpoints for the secondary objectives (2.0 and 2.1).

The safety endpoint was defined as a composite of:

- Cardiovascular death;
- Myocardial infarction;
- Stroke.

For all study objectives, information on myocardial infarction and stroke will be obtained from the EHR data, while information on death will be obtained from Datavant. Datavant compiles mortality data from government sources, obituaries, newspapers, and claims data for more than 90% of the U.S. population. Cause of death will be ascertained from the subset of individuals whose records can be linked to death certificates; otherwise, diagnoses adjacent to death will be identified, as feasible, using information from the EHR (e.g., cardiovascular-related hospitalizations or emergency department visits immediately preceding date of death).

A U.S.-licensed physician consultant, blinded to exposure, will review the detailed chronological listing of individual-level EHR data (and claims, where relevant) of a randomly selected subset of apparent MACE cases to determine whether MACE occurred. The adjudication process will compare the operational definition of MACE in the EHR to the physician's professional judgement and the occurrence of MACE in the EHR and claims data. If the initial EHR-based definition of MACE does not meet a pre-specified threshold for concordance, then adjustments to the initial list of diagnoses and procedure codes will be made to improve the accuracy of the operational definition of MACE.

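### The MACE case review checks only the composite, so a poorly measured component can pass unseen, and no check of a revised code list is specified

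*Combined protocol and SAP*

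**What the plan says.** Protocol section 6.5.2 describes the endpoint check in one paragraph. The physician reviews the longitudinal records "of a randomly selected subset of apparent MACE cases to determine whether MACE occurred". The comparison made is also at composite level: "The adjudication process will compare the operational definition of MACE in the EHR to the physician's professional judgement", together with the occurrence of MACE in the EHR and claims data. The trigger for action is a single one: "If the initial EHR-based definition of MACE does not meet a pre-specified threshold for concordance". The stated response when it is missed is a change of codes: "then adjustments to the initial list of diagnoses and procedure codes will be made to improve the accuracy of the operational definition of MACE". The section gives no number of cases, concordance measure or threshold value.

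The same section lists as secondary endpoints "Individual components of MACE, analyzed separately", and it measures the components differently: "information on myocardial infarction and stroke will be obtained from the EHR data, while information on death will be obtained from Datavant". Cause of death comes from the death certificate for those who can be linked; "otherwise, diagnoses adjacent to death will be identified, as feasible, using information from the EHR".

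No component-level sample, question or threshold appears in section 6.5.2, in the analysis sections (9.1 to 9.5), under quality control (9.6) or under limitations (10). Nor does a second review after a change to the code list.

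**The concern.** A random sample of apparent MACE cases holds mostly the commonest component. One pooled concordance figure is a share-weighted average, so good performance on MI and stroke can carry a component that is largely false positive. CV death is the obvious candidate, because part of it rests on diagnoses recorded near the date of death. Changing diagnosis and procedure codes would also not correct errors that come from certificate linkage.

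False-positive events that occur at the same rate in both groups pull the IRR toward 1. In a safety study that looks like reassurance. The harm falls mainly on the component endpoints and less on the primary composite. It concerns the IRR: false positives at equal rates cancel in the incidence rate difference (IRD) and only add noise to it.

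The second gap concerns the revised definition. If the threshold is missed, the adjusted list would define the primary endpoint, and the plan specifies no separate sample or re-test to show that the adjustment worked.

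**Working it through.** The plan states no figure for this review, so there is nothing to reproduce. The shares, PPVs, 80% threshold and review sizes below are assumptions.

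**1. Can a poor component pass?** Pooled PPV = sum of (share × PPV).
- Shares for MI, stroke and CV death of 55%, 30% and 15%, with PPVs of 92%, 85% and 50%.
- 0.55 × 0.92 + 0.30 × 0.85 + 0.15 × 0.50 = 0.506 + 0.255 + 0.075 = 0.836, which is above 0.80.

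**2. How much does this depend on the share?** Set MI and stroke at PPV 90% and CV death at 50%. The pass probability is the exact binomial chance that at least 80% of reviewed cases are confirmed. The last column applies the same rule to the CV deaths alone, taking their number as share × cases reviewed.

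| CV-death share | Pooled PPV | Pooled test passes (100 / 200 cases) | CV death alone passes (100 / 200 cases) |
|---|---|---|---|
| 10% | 0.86 | 0.96 / 0.99 | 0.055 / 0.006 |
| 20% | 0.82 | 0.75 / 0.80 | 0.006 / 0.0001 |
| 30% | 0.78 | 0.37 / 0.28 | below 0.001 / below 0.001 |

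The CV-death PPV at which the pooled value just equals 0.80 is (0.80 − (1 − w) × 0.90) / w, where w is the share. This gives 0.40 at w = 0.2, 0.57 at w = 0.3 and 0.65 at w = 0.4. At w = 0.1 it is negative: no CV-death PPV, however low, brings the pooled value below 0.80.

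**3. What does it do to the rate ratio?** Assume the same false-positive rate in both groups and let PPV be that in the lorcaserin group. Observed IRR = true IRR × PPV + (1 − PPV). For a true IRR of 2.0:
- CV death, PPV 0.50: 2 × 0.50 + 0.50 = 1.5.
- Any component, PPV 0.80: 2 × 0.80 + 0.20 = 1.8.
- Composite, PPV 0.836: 2 × 0.836 + 0.164 = 1.836, about 1.84.

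**4. How much does a pooled sample say about CV death?** At a 15% share, 100 reviewed cases hold about 15 CV deaths. If 8 of 15 are confirmed, the exact 95% confidence interval is 27% to 79%.

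**5. How many CV deaths are there to review?** Section 8.2 uses 2 MACE per 1,000 person-years, and the abstract gives about 37,000 + 16,000 = 53,000 initiators. That is 53,000 × 0.002 = 106 events per year of mean follow-up. Mean follow-up is not stated; at an assumed 1, 2 or 3 years there are 106, 212 or 318 events. At a 15% share, about 16, 32 or 48 are CV deaths. Equal allocation of 100 cases needs about 33 per component, so CV deaths may be too few for that, and for a fresh sample as well.

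**The case against.** Three objections carry weight.

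- **The size is assumed.** Every share, PPV, threshold and review size above is an input of this review. At a 30% CV-death share with PPV 50%, the pooled test would more often fail and so raise the alarm. This stands: a poor component can pass, and nothing shows that it will.
- **A component-level check is imprecise.** Confirming 27 of 33 gives a 95% interval of 65% to 93%. If half are held back, 13 of 16 gives 54% to 96%. With 16 cases, a component with a true PPV of 85% would miss an 80% threshold about 21% of the time. This also stands, and it argues for reporting intervals and for reviewing every apparent CV death if they are few.
- **Other safeguards exist.** The reviewer is blinded, and claims data are compared too. Blinding prevents differential judgement; it does not prevent one component from masking another. The claims comparison is stated for MACE as a whole and is not described as a re-test of a revised list. About 64% of NB initiators had linked claims at some time (section 8.1).

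A reader might go further and infer that the code list is tuned on the very cases reviewed, that the revised definition is never checked, and that it would be reported with an accuracy it lacks. The documents do not support this. They name no data source for the adjustment, describe no next step, and promise no PPV after revision; the sentence also cites published code-validation studies, which could guide a change. Nor does the text rule out a stratified random subset. A review of apparent cases alone would not find missed events, but the reach of the claims comparison is not stated, so it cannot be said flatly that missed events would stay hidden.

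**Conclusion.** The point holds as a design weakness that should be corrected, mainly for the secondary endpoints. As written, the sampled unit, the physician's question and the threshold are all at composite level, while the components are analysed separately and CV death is measured by a different route. Under the assumed inputs, a component with PPV 50% sits inside a passing pooled PPV of 0.84, and its true IRR of 2.0 appears as about 1.5. The composite is affected less, at about 1.84. These figures rest on non-differential false positives and on the component being a small share of cases.

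For a revised code list, the finding is limited to this: no separate sample or re-validation is specified.

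**What to change.** Change section 6.5.2 as follows.

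- Stratify the blinded review sample by component and, for death, by cause-of-death route (linked certificate or adjacent diagnoses). Review all apparent CV deaths if they are few.
- Ask the physician whether the specific component occurred.
- State the number of cases, the concordance measure and the threshold. Report PPV with a confidence interval and apply the threshold for each component. Reweight by stratum share to obtain the composite PPV.
- If a list is revised, confirm it on reviewed cases not used for the revision, where numbers allow.
- Freeze the definition before any events are counted by treatment group.
- Where a component stays below the threshold, report its IRR and IRD with a PPV-based sensitivity correction. Under a common false-positive rate, the corrected IRR is (observed IRR − (1 − PPV)) / PPV, with PPV from the lorcaserin group; for example, (1.5 − 0.5) / 0.5 = 2.0. A single PPV applied as a multiplier to both groups would leave the IRR unchanged and so would not serve.

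The cost is protocol wording and a reallocation of roughly the same workload by the same physician. The downsides are slightly less precision for the composite PPV, wide intervals for CV death, and part of the review held back for confirmation.

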	
Inclusion and exclusion criteria for the main objective will ensure that only new users are included, and that the NB and comparison groups are comparable on risk factors for MACE after application of propensity score (PS) matching weights.
 
Inclusion and exclusion criteria for the additional objectives will align with those used in the 2018 trial assessing cardiovascular endpoints among lorcaserin users, insofar as the data support a comparable replication.
		
Variables:	
The key variables are initiation of NB, initiation of lorcaserin (active comparator), time on treatment, and the endpoint of MACE. The individual components of MACE will also be quantified. Covariates will be derived from clinical measurements, past medical history, diagnoses, observations, and prescription records. Multiple imputation will be applied to address missing data, coupled with PS analyses to address confounding.
		
Data Sources:	
EHR and linked claims data from Arcadia Data Research. The data currently cover approximately 75 million people in the U.S.
		
Study Size:	
There are approximately 37,000 apparent NB initiators in the Arcadia data.
 
There are approximately 16,000 apparent lorcaserin initiators.
		
Data Analysis:	
Descriptive statistics of the study cohorts, multiple imputation of missing covariates, estimation of crude incidence rates of MACE among initiators of NB, and adjusted incidence rates of MACE after applying PS matching weights will be calculated (1.0 and 1.1). Analogs to intention-to-treat and per-protocol cohort analyses will be conducted. The analysis will also follow the principles of the RCT DUPLICATE Initiative (2.0 and 2.1) to assess the concordance between findings in an EHR study to those in the lorcaserin cardiovascular safety endpoints trial. In addition, we will conduct a case-crossover study to assess the effects of NB on MACE (2.2) and other sensitivity analyses.
		
Milestones:	
 
 Start of Data Collection End of Data Collection	September 2014 February 2020	
 
	Start of Data Collection End of Data Collection	September 2014 February 2020
Start of Data Collection End of Data Collection	September 2014 February 2020		

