## 5 RESEARCH QUESTIONS AND OBJECTIVES

The study will assess whether patients who initiate treatment with NB are at an elevated risk of MACE compared with patients who initiated treatment with lorcaserin, an active comparator chosen to reduce potential confounding. Lorcaserin was approved in the U.S. under the brand names BELVIQ® and BELVIQ XR® for the same indication as NB, and withdrawn from the market due to cancer safety concerns in 2020. Lorcaserin is not believed to have adverse effects on cardiovascular outcomes. The CAMELLIA-TIMI 61 trial was a comparison of lorcaserin relative to placebo in overweight and obese patients with cardiovascular disease and cardiovascular disease risk factors. The trial found no difference in the rate of cardiovascular events.

The study's main objective is to compare the incidence of the primary endpoint (MACE) between initiators of NB and initiators of lorcaserin (1.0). The study will also compare the incidence of the secondary endpoint, consisting of each *component* of MACE, between initiators of NB and initiators of lorcaserin, across the following subgroups (1.1):

- Patients with obesity (i.e., most recent BMI measurement  $\geq 30$  kg/m^2);
- Patients with a diagnosis of hypertension, regardless of BMI;
- Patients with a diagnosis of type 2 diabetes mellitus, regardless of BMI;
- Patients with a diagnosis of dyslipidemia, regardless of BMI.

The study's additional objectives aimed at testing the robustness of the methods are:

- To assess the comparability of findings from an EHR study to those of a 2018 clinical trial, aligning with the RCT DUPLICATE Initiative (2.0);
- To quantify differences in cardiovascular safety endpoints between the clinical trial and the results of this EHR study (2.1);
- To conduct other sensitivity analyses, including a self-controlled, case-crossover analysis to quantify the potential effect of NB on MACE (2.2).

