## 6 RESEARCH METHODS

### 6.1 Study Design

A retrospective cohort study design will be used for the main objective and endpoints. Initiators of NB will be identified between September 2014 and February 2020. Contemporaneously, we will identify all lorcaserin users between 2012 and 2020. A self-controlled, case-crossover design will be used for the sensitivity analysis (2.2).

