Follow-up time will be calculated separately for each study endpoint. Patients will be followed starting the day after initial exposure until the first of the following censoring events: (1) the study endpoint of interest, (2) death (for those who do not have the endpoint of interest), or (3) end of available data for those who do not have the event of interest (i.e., censoring due to end of available EHR data). Person-time will be calculated by summing the days from cohort entry (day 0) to the date of the first relevant censoring event.

To test the robustness of assumptions about the date of censoring, analyses with differing censoring definitions will be performed, and estimates compared:

- To assess whether the censoring date needs to be adjusted, the physician consultant will review a random sample of patient health profiles to determine whether there is a clear indicator of censoring. Insofar as there appears to be a clear indicator of censoring, the physician will record this date (blinded to exposure), and this information will be used to

adjust the censoring date. Indeed, this information may be treated as an annotation for a machine learning model.

- To account for a patient still being on the insurance plan but not accessing the healthcare system, adjust the end of follow-up to be 6 months, 1 and 2 years following their last healthcare encounter in the EHR.
- To assess the reliability of our method for computing time until censoring in the EHR, compare follow-up times in the EHR to those observed in the claims enrollment files using a subset of those with EHR and claims data.
- To test robustness of the method for computing follow-up time in the EHR, compute the distribution of follow-up times based on enrollment spans within the subset of individuals with claims and EHR data and apply the median follow-up time within populations with particular health profiles.
- To implement a more specific definition of follow-up time, assume that a last healthcare encounter with a primary care provider, endocrinologist, or geriatric care provider in combination with no death information is the end of enrollment.

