### 8.1 Study Size

According to the most recent available data from Arcadia (delivered to Exponent November 2022), ~37,000 patients had an apparent initiation of NB. Of those patients ~64% had linked, adjudicated claims data at some point in time. Seventy percent of apparent initiators were women.

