### 9.5.2 As-Treated Analysis

The ITT analysis will be juxtaposed with analyses of person-time classified by actual exposure to NB and lorcaserin, grouped into categories of current, recent, and past use. These person-time classifications estimate the effect of being on (or off) the treatment on the rate of the outcomes. Such estimates are often desirable for drug safety questions because they avoid misclassification of exposure that arises in ITT analysis; however, the balance introduced at baseline by PS matching weights may deteriorate as patients switch non-randomly among different study drugs. Therefore, the ITT and *as-treated* analyses are best interpreted together.

To obtain the hazard ratios necessary to compare trial results to those obtained through use of RWD, we will use an ITT analysis for the primary analyses, and as-treated for sensitivity analyses, as was done in the CAMELLIA-TIMI 61 trial.

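### The end of follow-up is not fixed; if it runs past lorcaserin's 2020 withdrawal, the later part of as-treated current-NB time has essentially no concurrent comparator

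*Combined protocol and SAP*

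**What the plan says.** Three statements bear on when observation ends.

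- Abstract (section 3), Milestones: the entries "Start of Data Collection End of Data Collection" carry the dates "September 2014 February 2020".
- Section 6.5.2: follow-up stops at the endpoint, at death, or at the "end of available data for those who do not have the event of interest (i.e., censoring due to end of available EHR data"). No calendar date is attached.
- Section 8.1: the initiator counts come from the "most recent available data from Arcadia (delivered to Exponent November 2022").

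Section 6.1 uses the abstract's dates for something else: "Initiators of NB will be identified between September 2014 and February 2020". There they are an entry window for NB, not an end of follow-up.

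On the comparator, section 5 says that lorcaserin was "withdrawn from the market due to cancer safety concerns in 2020", with no month. Section 6.5.1 closes lorcaserin entry at withdrawal. Section 9.5.2 plans "analyses of person-time classified by actual exposure to NB and lorcaserin, grouped into categories of current, recent, and past use", with no calendar limit. Section 9.4 names calendar time only at the start of treatment, in the paragraph on the trial-comparability cohort. The Poisson model in section 9.5.3 has no term for calendar period during follow-up.

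**The concern.** Under the section 6.5.2 rule and the 2022 extract, NB patients can remain current users for up to about 32 months after lorcaserin has gone. Lorcaserin patients cannot, apart from any supply left from late prescriptions. The current-use rate for NB then averages over an earlier and a later calendar period, while the rate for lorcaserin comes from the earlier period alone. Weights fixed at baseline do not correct this, because two patients who start in the same month can contribute current-use time in different calendar periods.

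If MACE incidence, care-seeking or recording in the EHR changed after withdrawal, the as-treated current-use IRR and IRD would absorb that change as if it were an effect of NB. The direction is unknown in advance: a fall in recorded events would make NB look safer, and a rise would make it look worse. The end date should be settled before the results are known, because it affects a safety estimate intended for FDA (section 13).

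**Working it through.** **Plan's own figure.** The plan quantifies nothing on this point. Its nearest figure is power above 80% for a relative risk of 2.0 (section 8.2). The text gives no alpha or mean follow-up and Figure 3 is not shown, so exact reproduction is not possible. At two-sided 0.05, 2 events per 1,000 person-years and 37,000 against 16,000 initiators, 80% is reached at a mean follow-up of about 0.43 years (Schoenfeld) or 0.55 years (two proportions). With 16,000 per arm it is reached at 0.68 years. The claim is plausible and is not in dispute here.

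**Inputs from the documents.** NB entry September 2014 to February 2020, taken as A = 5.5 years (66 months). Extract delivered November 2022, taken as B = 2.667 years (32 months) after the end of February 2020. NB initiators 37,000. MACE rate 2 per 1,000 person-years.

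**Assumptions not in the documents.** Uniform entry; withdrawal at about the end of February 2020; data running to the delivery month; exponential time on drug with mean m; no loss to follow-up.

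**Formulas.**
- Proportion still on drug at the end of February 2020: p = (m/A)(1 - exp(-A/m)).
- With q = exp(-B/m), the post-withdrawal share of current-NB time is s = p(1 - q)/(1 - pq).
- If the later event rate is c times the earlier one and the true IRR is 1, the apparent IRR is 1 + s(c - 1).

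For m = 0.5: p = 0.0909 and q = 0.0048, so s = 0.0909 x 0.9952/0.9996 = 0.091.
For m = 1: p = 0.1811 and q = 0.0695, so s = 0.1811 x 0.9305/0.9874 = 0.171.

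| Mean use (years) | s | Expected NB MACE in that time | Apparent IRR, c = 0.8 | Apparent IRR, c = 1.5 |
|---|---|---|---|---|
| 0.25 | 4.5% | 0.8 | 0.991 | 1.023 |
| 0.5 | 9.1% | 3.3 | 0.982 | 1.045 |
| 1 | 17.1% | 12.5 | 0.966 | 1.085 |
| 2 | 27.5% | 37.1 | 0.945 | 1.138 |
| 3 | 33.3% | 59.9 | 0.933 | 1.166 |

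Counting 65 and 33 months instead gives 9.2% and 17.4% for the second and third rows. If follow-up ends in February 2020, s is zero.

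**ITT.** With no loss, the NB share of ITT time after February 2020 is B/(A/2 + B) = 2.667/5.417 = 49%. For lorcaserin initiators entering uniformly from the start of 2012 or of 2013, it is about 40% or 43%. Both arms are therefore observed in the later period.

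**Cost of ending current-use time at withdrawal.** For a rate ratio of 2.0 (Wald test on the log rate ratio, unweighted arms, lorcaserin entry from mid-2012 assumed), m = 1 gives 27.8 lorcaserin events and 146.1 NB events, falling to 121.2 NB events when truncated. Power goes from 0.918 to 0.909. At m = 0.5 it goes from 0.686 to 0.679.

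**The case against.** **The premise may be false.** The abstract ends data collection in February 2020; if that is the cut-off for follow-up, the problem largely disappears. November 2022 is a delivery date, not a date through which data are complete, and Figure 1, which is not shown, may mark the end of follow-up. All of this stands, and it makes the bias conditional. It does not settle the cut-off: section 6.5.2 is the operative rule and gives no date, and section 6.1 allows the February 2020 milestone to be read as an entry window.

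**The effect is small beside sampling error.** At mean use of 6 to 12 months there would be about 37 to 74 NB and 16 to 32 lorcaserin events at the planning rate. The 95% interval is then roughly the estimate multiplied and divided by 1.8 to 1.5. Section 9.5.2 also admits non-random switching and asks that ITT and as-treated results be read together. This stands as to size. Reading the two together does not remove a calendar imbalance from one of them.

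**Stronger readings that the documents do not support.**

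- A reader might infer that all as-treated NB time lacks a concurrent comparator, or that switching runs only toward NB throughout. Both apply only after withdrawal. Before it, lorcaserin use is concurrent, and section 9.5.1 foresees switching without stating a direction.
- A reader might infer that past-lorcaserin time is mostly stopping forced by the market. With mean use of 6 to 12 months, only about 9-18% of initiators would still be on drug at withdrawal (p above), and fewer if entry starts in 2012. The rest would already have stopped.
- A reader might put a figure on ITT dilution. For example, if half of lorcaserin time is post-withdrawal and 10% of that is spent on NB, a true 2.0 reads as 2/(1 + 0.5 x 0.1) = 1.90. That sum keeps the NB arm at doubled risk throughout, yet with mean use of 6 to 12 months NB patients would be on drug for only about 9-18% of ITT time (0.5/5.417 to 0.987/5.417). The 10% has no source in the documents. Section 6.4 also randomly assigns patients prescribed both drugs to a baseline group, so contamination need not be confined to one arm.

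**Conclusion.** The point holds in a limited form, as something to correct before analysis. The documents conflict on when follow-up ends. Under the section 6.5.2 rule, the post-withdrawal part of as-treated current-NB time has essentially no concurrent current-lorcaserin time, and nothing in the plan adjusts for calendar time of follow-up.

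The size is modest: about 9-17% of current-NB time at mean use of 6 to 12 months, with a wider range of 5-33% for 3 months to 3 years. At 6 to 12 months, a true IRR of 1.0 reads about 0.97-0.98 for an assumed 20% lower later rate, or 1.05-1.09 for an assumed 50% higher one. Persistence, uniform entry, the withdrawal month, the last data month and the rate changes are all assumptions.

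The ITT contrast has concurrent follow-up in both arms. After withdrawal, any switching between the study drugs can run only toward NB, but the size of that effect cannot be derived from the documents.

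**What to change.** 1. State one administrative end date in section 6.5.2, and reconcile the abstract's milestones and section 8.1 with it. Give the withdrawal month used.
2. If follow-up runs past withdrawal, either restrict the as-treated current-use contrast in both arms to calendar time up to withdrawal, or add a calendar-period term to the as-treated Poisson model. Restriction needs no modelling; the period term assumes a period effect common to the exposure categories.
3. Keep recent- and past-use time after withdrawal, with the period term. Both drugs contribute such time, so cutting it off would discard concurrent comparison.
4. Report the ITT IRR with both arms ended at withdrawal as a sensitivity analysis beside the full-follow-up IRR.

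The cost is SAP wording and one extra run. Restricting current use loses some NB person-years, with a power change of about 1 point or less in the calculation above. The truncated ITT analysis will have wider intervals.
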